 - x. Short form health survey form (SF-12)
 - xi. EQ5-D
 - xii. Stages of Change Questionnaire in Weight Management (S-Weight)

b. Parents:

- i. Demographic Screen
- ii. Health Encounters
- iii. Parent Satisfaction Survey

Outcomes:

	0	3	6	12	18
Study Visit Window of Completion		+/- 2 weeks	+/- 2 weeks	+/- 4 weeks	+/- 4 weeks

Covariates:

Demographic Information	x				
Youth's Perceived Stress Score	x	x	x	x	x
Family Member's BMI	x			x	x

Primary Outcomes:

BMI Status Change- %BMIf95	Height, Weight, zBMI,	x	x	x	x	x
-------------------------------	-----------------------	---	---	---	---	---

Secondary Outcomes:

Adherence-	x	x	x	x	x	
Satisfaction- Satisfaction Survey	x	x	x	x	x	
Fasting Lab Tests-	x		x		x	
Cost Analysis- Encounters*	Health Care	x	x	x	x	x

Mediators:

Addictive eating qualities- YFAS and FCQ	x	x	x	x	x
Self-Regulation- ASRI	x	x	x	x	x
Executive Function- BRIEF 2	x	x	x	x	x

*An official Health Care Encounters questionnaire will be completed by the parents at in-person/WebEx study visits at 0, 3, 6, 12, and 18 months post consent. Additionally, all participants will receive a call monthly from a study team member during the study period. In these calls weight outcomes, barriers and any interim health encounters (physician visits, diagnosis, medication prescribed etc.) occurred in the previous 4 weeks will be assessed.

3. All consenting participants:

- a. AppCoach and AppAlone arms will receive:
 - i. Loaned iPhone (app is iOS compatible only) if the participant does not already have one
 - ii. Wireless Bluetooth body weight scale
 - iii. Digital food scale
 - iv. Measuring tape (if participating virtually)
- b. In Clinic arm will receive:
 - i. Digital body weight scale
 - ii. Measuring tape (if participating virtually)
- c. Participants in the AppCoach and App arms who require an iPhone will be loaned an iPhone and accessories (including protective case), with an AT&T service plan for the 6-month intervention of the study that includes: unlimited texting, unlimited plan, unlimited voice calls to and from other cell telephones, 700 voice call minutes for calls to and from landlines, unlimited night and weekend calls to and from landlines, International calls or texts including Canada are NOT allowed and not covered. iPhones will be returned at the completion of the intervention (visit 3: 6-month follow-up visit/mail equipment back to study team).

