- d. One parent will complete the above-mentioned questions and have their height, weight and BMI measured/self-reported at consent and at 18-month follow up (end of study).

3. AppCoach and AppOnly Participants:

- a. Each participant will be registered with their email address via a computer and then login with the app.
- b. Participants will weigh-in on a scale in a private area and enter weight data into their iPhones. Participants will weigh themselves and their food daily. This information will be automatically synced (entered) into the app. However, if the wireless scales are not used, they will need to enter the information manually into the app.
- c. A study team member will go through each section of the App and have participants enter data.
- d. Follow-up: participants will schedule in-person/WebEx study visits at 3, 6, 12 and 18 months. Participants will also have the option of conducting visits virtually via WebEx and/or receiving survey links via email directly from REDCap.
- e. AppCoach participants will also schedule weekly 15-minute phone meetings with a coach in addition to follow up study visits in-person/WebEx visits at 3, 6, 12 and 18 months.

4. In Clinic Participants:

- a. Each participant will attend a multi-disciplinary in-clinic or WebEx intervention consisting of 6 sessions (120 minutes +/- 30 minutes); one session per month for 6 months.
- b. They will meet with several members of the provider team throughout the intervention: physical therapist, psychiatrist, Registered Dietitian, health educator, physician and research team.
- c. Participants will be weighed or provide a self-reported weight at every session and follow up visits
- d. Participants will have the option of weighing themselves daily.
- e. Follow-up: participants will attend in person/WebEx follow-up visits at months: 3, 6, 12, and 18
- f. Participants will be provided a KNF newsletter for sessions 1-6. The newsletters summarize what was discussed during the session they attended. They will also be provided with a height and weight measurement tool. The newsletter and tool will be emailed or texted.

5. Research Blood Draws (all arms):

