- 3) The site is within mobile phone range on the other hand, a trial site will be ineligible if it satisfies one or more of the following conditions:
 - 1) The principal investigator withdraws consent for participating in the study.
 - 2) The steering committee of the present trial judges the site to be inappropriate to recruit participants.

Initial trial sites include: CHLA, Los Angeles Biomedical Research Institute at Harbor-UCLA (LA Biomed), UCLA, and Cedars Sinai.

Site Training:

Each on-site CRC will receive 8 hours of training prior to recruitment start date.

Study Design:

404 reflect the 190 youth and 190 parent/guardians plus the 12 youth and 12 parent/guardian subjects that will be enrolled for the pilot study at CHLA.

We are aiming to recruit a total of 292 youth total with 1 parent/legal guardian per youth (total of 584 including the parent/guardian in the subject accrual number + 12 pilot youth + 12 pilot parent/guardian).

We plan to enroll 584 participants (youth & parent/guardian) into each intervention arm as follows:

[figure not shown]
CHLA/AltaMed = 404 (Pilot: 12 youth + 12 parent/guardians; Open enrollment: 190 youth & 190 parent/guardians)

UCLA = 60 (30 youth & 30 parent/guardians)

Harbor UCLA = 60 (30 youth & 30 parent/guardians)

Cedars Sinai = 60 (30 youth & 30 parent/guardians)

Pilot Group: We plan to initially recruit 12 patients from the CHLA EMPOWER clinic. The patients will be randomized to the three intervention arms and will complete a 2-month trial to assess intervention fidelity of the curriculum and identify any potential difficulties. The pilot subjects are reflected in the information above. .

Assessments:

Anthropometric Data

Height and weight will be assessed at in-person visits by study team member or self-reported if visit is conducted virtually via WebEx. Height will be measured using a Quick Medical stadiometer, accurate to 0.1 cm (Quick Medical, Issaquah, WA). Weight will be measured on a self-calibrating Mobile Stand Digital Scale,

accurate to 0.1 kg. Participants will wear minimal clothing during the height and weight measurements. BMI will be calculated as kilograms per square meter and BMI Z-score (zBMI) and percent over the 95th percentile (%BMI_{p95}) will be determined utilizing the CDC growth charts.

Physical Activity

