Coaches will have undergraduate training and be highly knowledgeable about motivational interviewing clinical practice guidelines regarding strategies for obesity management in youth. Coaches will be taught to table unfamiliar clinical and counseling questions, which may arise during coaching. They will then discuss these questions with [name] (AV) at bi-monthly team meetings, who will provide direction about management on future calls. Coaches will record all calls, and AV and SS will review a subset of these

recordings. Coaches will receive monthly feedback regarding implementation of directive and nondirective coaching modes.

Clinic: Multi-Disciplinary In-Clinic Monthly Intervention (In-Clinic Group)

The team consists of a coordinator/health educator, physicians (MD), registered dietitian (RD), physical therapist (PT) and psychologist, who will assess participants in a clinic setting/virtually, with monthly visits with one or more providers (averaging 100 minutes at the initial visit and 80 minutes per follow up visit, ~8 contact hours per participant per 6-month intervention period). Core principals of the clinic include motivational interviewing (MI) and family-centered care. Patients and their parent/guardian are expected to attend monthly clinic visits for at least six visits (6 months). The study team member will obtain height and weight at the beginning of each visit.

The coordinator/health educator will evaluate the patient and families overall emotional health and address anxiety, psychosocial stressors, and emotional eating. Healthy eating goals focus on hunger management, portion control, decreasing sugar-based beverage intake, increasing fruit and vegetable intake, and modifying eating behaviors. Changes in behavior for the entire family are strongly encouraged. The multi-disciplinary team utilizes treatment strategies that include MI, nutritional education, and behavioral therapies targeted at improving daily routines, emotional health, sleep quality and quantity, diet, and physical activity. Each team member documents the patient's goals identified at each visit and distributes a summary check-out document to the team and the family. Goals for healthy eating, increased physical activity, better sleep habits, emotional well-being, and family support are then followed up at subsequent monthly visits.

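### Height and weight for the primary outcome are staff-measured in person but self-reported at virtual visits, and nothing in the plan handles a change of mode within a participant's change score.

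*Combined protocol and SAP*

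**What the plan says.** All sections are in the combined protocol and SAP.

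- **Assessments, Anthropometric Data.** Staff take height and weight when the visit is in person; otherwise the values are "self-reported if visit is conducted virtually via WebEx". The in-person tools are a stadiometer accurate to 0.1 cm and a self-calibrating scale accurate to 0.1 kg.
- **AppCoach and AppOnly Participants.** "Participants will also have the option of conducting visits virtually via WebEx". Nothing ties a participant to one mode. The Initial Visit section also allows a virtual baseline, and Clinic follow-ups may likewise be in person or by WebEx.
- **In Clinic Participants, item c.** "Participants will be weighed or provide a self-reported weight at every session and follow up visits". The description of the multidisciplinary Clinic intervention, whose visits may also be virtual, says instead: "The study team member will obtain height and weight at the beginning of each visit". The two statements differ on whether Clinic-arm weight is always obtained by staff.
- **Supplies by arm.** The two app arms receive a "Wireless Bluetooth body weight scale", the Clinic arm a "Digital body weight scale". The tape is conditional in every arm: "Measuring tape (if participating virtually").
- **Research Blood Draws.** All arms have a draw at months 6 and 18. A baseline draw is done where recent routine results are not available. None is linked to anthropometry.
- **Outcomes.** Change in zBMI and %BMIp95 is primary, both within and between groups.
- **Statistical Analysis.** The models name recruitment site, demographic characteristics and questionnaire scores, but not measurement mode. The nearest check is a pair of per-protocol subsets, completed before or during COVID, defined by calendar date.

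**The concern.** A change score removes a constant reporting error only when both of its values carry that error. If baseline is measured on a stadiometer and calibrated scale and follow-up is self-reported, the whole error enters the change. The plan permits this pattern and gives the analyst no stated way to detect it.

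Two results are exposed. Within-group change is biased whenever mode switches and self-report is off on average. The between-arm contrast is biased if the frequency of switching, or the error made on switching, differs by arm. The arms have different contact patterns (9 visits in Clinic, 5 in each app arm), so equal switching between AppCoach and Clinic cannot be taken for granted. The documents do not say which arm would switch more.

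**Working it through.** **1. The plan's own figures.** Power and Sample Size Estimates gives, for AppCoach versus Clinic, 0.040 zBMI at effect size 0.580 (88% power) and 4.08 %BMIp95 points at effect size 0.625 (92% power). The implied SDs of change are 0.040/0.580 = 0.069 and 4.08/0.625 = 6.53. A two-sample t-test, two-sided 5%, with 60 per arm gives 88.3% and 92.4%, which matches. (With 97 per arm, from 292 in three groups, it gives 98.0% and 99.1%.) The stated powers therefore rest on 60 per arm, the number in Statistical Analysis, and I use 60 below.

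**2. Shift in one participant's change score.** Assumption: 1 kg under-report and 1 cm over-report at follow-up only.

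Shift = 100 × [w/h² − (w − 1)/(h + 0.01)²] / P95, where P95 is the 95th-percentile BMI. Body sizes and P95 are assumed.

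| Weight, height | BMI measured | BMI reported | Shift at P95 = 26 / 28 / 30 |
|---|---|---|---|
| 85 kg, 1.62 m | 32.39 | 31.62 | 2.97 / 2.76 / 2.58 |
| 95 kg, 1.65 m | 34.89 | 34.11 | 3.01 / 2.79 / 2.61 |
| 105 kg, 1.70 m | 36.33 | 35.57 | 2.94 / 2.73 / 2.55 |

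The range is 2.55 to 3.01 points. It varies body size, not the error. Varying the error at 165 cm, %BMIp95 of 120 and P95 of 28 gives:

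| Assumed error | Shift (%BMIp95 points) |
|---|---|
| 1 kg alone | 1.3 |
| 1 cm alone | 1.4 |
| 1 cm + 1 kg | 2.7 |
| 2 cm + 1 kg | 4.1 |
| 2 cm + 2 kg | 5.4 |

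For zBMI, 1 cm + 1 kg gives about 0.05 to 0.07 at %BMIp95 of 120, over an assumed range of growth-chart (LMS) parameters.

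**3. Bias in the arm contrast.** Bias = mean shift × difference between arms in the proportion who switch. With a mean shift of about 2.8 points:

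- 25 percentage points: 2.8 × 0.25 = 0.7, and 0.7/4.08 = 17%.
- 50 percentage points: 2.8 × 0.50 = 1.4, and 1.4/4.08 = 34%.

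For zBMI, the same differences times 0.05 to 0.07 give 0.013 to 0.018 and 0.025 to 0.035, against 0.040 sought. This rests on the assumed LMS values as well.

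**4. False-positive rate if there is no true difference.** The standard error at 60 per arm is 6.53 × √(2/60) = 1.19. Biases of 0.7 and 1.4 are 0.59 and 1.17 standard errors. The noncentral t then gives rejection rates of about 9% and 21% against a nominal 5%. At 97 per arm the standard error is 0.94 and the rates are about 12% and 32%, because a larger sample does not dilute bias. The SD is held at 6.53 throughout.

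**5. Equal switching in all arms.** The bias in the contrast is zero, but variance rises. If half of each arm switches, %BMIp95 power at 60 per arm goes from 92% to about 90% (shift mean 2.8, SD 2, assumed). zBMI power goes from 88% to about 72% (shift mean 0.07, SD 0.05, assumed).

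**The case against.** Several points on the other side stand.

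- A reader might set the 2.6 to 3.0 point shift beside the 2.80 points sought for AppCoach versus App and conclude that mode alone could produce the effect. That compares one youth's shift with a difference in group means. A bias of 2.80 from a 2.8-point shift would need everyone in one arm and no one in the other to switch. Those two arms also share the same scale, the same study-visit schedule and the same virtual option, so the documents give no arm-specific reason for imbalance there.
- A reader might infer that different home scales bias the contrast. A scale difference cancels in a change score if the same scale is used at both visits. Calling all self-reported weights unverified would also be too strong: app-arm weights can sync from the scale. However, manual entry is allowed, nothing says the synced weight becomes the visit value, and height has no device record in any arm.
- Payment gives no stated motive to misreport. It rewards visits, weigh-ins, contact and app use, not weight lost.
- The extra Clinic visits number four (9 against 5) and may themselves be virtual, so they imply no direction for the imbalance.
- The error is assumed. Virtual participants have a scale and a tape, so their values may be readings rather than recall, and tape error need not be upward.
- The data forms are not shown, so mode may already be recorded. The pre- and during-COVID subsets partly track it. But they are defined by date and restricted to per-protocol participants, and the later subset can still mix switched and same-mode change scores.

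These points limit the size and direction of the problem. They do not supply a rule for handling a switch of mode.

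**Conclusion.** The point holds in limited form. As written, the plan lets staff-measured and self-reported values enter the same primary change score with no observed reading, no constancy of mode and no adjustment. Its two statements on who obtains Clinic-arm weight also need to be reconciled.

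Bias in within-group change requires only that some youths switch and that self-report is off on average. Bias in AppCoach versus Clinic also requires switching or error to differ by arm. The plausible size there is a fraction of the effect sought, enough to roughly double or quadruple the nominal 5% error rate in the two scenarios shown. Equal switching with equal error adds only noise to the contrast. The misreporting error, the body sizes and growth-chart values, and the switching proportions are all assumptions. The documents support neither a claim that the contrast is biased nor a direction for any bias. This should be corrected; confidence is medium because the main quantities are unknown.

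**What to change.** 1. At virtual visits, replace self-report with a weigh-in on the study-issued scale and a tape height, both observed live on WebEx. Give a tape to anyone who moves to virtual visits after an in-person start, since tapes are now supplied only to virtual participants.
2. Have staff measure height and weight at the research blood draws already planned at months 6 and 18, and at the baseline draw at CHLA where one is done. Use those values when the corresponding study visit is virtual. This covers the week-24 comparison; step 1 covers months 3 and 12.
3. Record mode at every visit. Add a sensitivity analysis restricted to youths whose baseline and follow-up values share one mode. Label it as sensitivity only: follow-up mode is determined after randomisation, so the restriction can itself disturb the randomised comparison. For the same reason, do not put mode in the primary model as a covariate.

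Do not carry the last measured height forward. Participants aged 14 to 18 may grow over 18 months, and there is no measured height to carry after a virtual baseline.

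Statistical Analysis is written in the past tense. If visits are already complete, recover mode from visit records and do step 3 alone.

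The cost is a few minutes per visit, some extra tapes, one form field and one additional analysis.
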